Study Title: A Health System Wide Evaluation of Mandated Use and Clinical Decision

Support Tools to Improve PDMP Utilization and Patient Outcomes

NCT Number: NCT04918355

Document Date: 3 December 2021

COMIRB Protocol

COLORADO MULTIPLE INSTITUTIONAL REVIEW BOARD
[name]
[contact] [contact]

Protocol #: **19-1130**

Project Title: A Health System Wide Evaluation of Mandated Use and Clinical Decision Support Tools to Improve PDMP Utilization and Patient Outcomes

Principal Investigator: [name], DO

Version Date: 3 December 2021

I. Hypotheses and Specific Aims:

Prior research by this team has shown that when emergency department (ED) prescribers are less likely to prescribe an opioid analgesic to patients at high-risk of overdose or misuse when they consult the Colorado Prescription Drug Monitoring Program (PDMP). Despite extensive work to reduce workflow and accessibility barriers to use of the PDMP, the majority of providers still do not use the PDMP when making prescription decisions. Clinical decision support (CDS) that is embedded in the Electronic Health Record (EHR) has promise as a tool to increase PDMP use, advance presentation of important PDMP data to providers and improve opioid safety without interrupting provider workflow.

This cluster-randomized study is designed to determine if:

- CDS tools that deliver focused, timely clinical information to prescribers can improve use of the PDMP
- The use of focused CDS tools can decrease high-risk opioid prescribing
- The use of focused CDS tools is associated with better patient outcomes: decreasing high-risk, long-term, and aberrant opioid use

Specifically, we will test the hypotheses that:

[figure not shown]
1. Use of a focused CDS tool will increase the percentage of high-risk patients who are checked in the PDMP in the target populations, compared to those who have not implemented the tool.
2. Use of a focused CDS tool will decrease the percentage of high-risk patients who receive a controlled medication prescription in the target populations, compared to those who have not implemented the tool.

II. Background and Significance:

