 - Although this condition is termed “mandatory” use, it is not a hard stop. The provider can easily close the window without consulting the PDMP and the prescription can be signed whether the PDMP has been consulted or not. The BPA will be built to track utilization of the BPA vs. bypass. Note: This has been deemed too interruptive for

[figure not shown]

Figure 2: Example BPA used in prior study.

ambulatory clinics and they will not be included in this arm.

3. Arm 3: CDS for high risk patients based on PDMP data
 - Based on initial interviews with providers (see 19-3063) CDS support will be designed to be supportive of provider workflows via interruptive alerts (BPAs) for high-risk patients only. No alerts will fire for patients without high risk indicators based on data in the PDMP or prescription history as shown in Epic. An example is given below. Exact phrasing may be modified during final testing in order to streamline appearance of the alert.
 - Again, BPA will be triggered upon entry of an opioid or benzodiazepine prescription and will fire only for patients determined to be at risk for controlled medication associated adverse events, misuse or overdose, based on logic built to identify high-risk characteristics. Definition of these risk characteristics is based on CDC guidelines and include: NarxCare opioid or overall overdose risk score (PDMP based) indicating the patient is in the highest ~5% of the population for controlled medication risk, initiating opioid treatment with an extended or long acting release formulation with no opioid usage in the previous 100 days, or information in the PDMP or EHR indicating overlapping opioid use or co-prescribing of a sedative with an opioid.
 - One-click access to the PDMP for all patients will be maintained as in other arms. If the provider reviews the PDMP during the encounter before prescribing, the BPA will be suppressed.

- As in Group 2, this is not a truly mandatory check and can be bypassed. BPA messaging was determined based on work with providers to deliver the most useful and clear information.
- The text displayed in the alert will be specific to the patient. BPA logic and phrasing is included in Appendix A.

[figure not shown]

Figure 3: Sample alert.

4. Arm 4: CDS for high risk patients based on PDMP and/or clinical characteristics

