Activation of the alert will be monitored using automated tracking within Epic which identifies providers and patients associated with alert firings. A key feature of the CDS is that the PDMP check must be "attested" to in order to suppress the CDS and prevent re-firing of the alerts, which is interruptive to the provider. This attestation is a workflow change for providers and is essential for CDS success. It can happen prior to prescription entry, in which case the alerts will not activate (suppression), or after activation of the alert.

In the event that providers are being "hit" with CDS alerts multiple times within the same encounter for a single patient because they miss the attestation step, an educational message with a link to the education website will be sent to the provider via email or EHR internal messaging systems to remind the provider to click the attestation button in order to prevent multiple firings. A weekly tally of messages sent will be retained, but no patient information will be retained. No provider will receive more than three educational reminders. The reminder will not include any patient information. This check is intended only to provide an additional personalized education step.

This is important because (1) dissemination of education about new CDS across all of UCHealth is challenging so we will miss providers and (2) we have concerns that if providers find the CDS to be a nuisance (due to a simple knowledge gap of not understanding the attestation requirement) they will not use the CDS.

Similarly, if a provider receives multiple alerts but does not access the PDMP in response, a reminder will be sent that checking the PDMP requires the same number of "clicks" as dismissing the alert and is considered best practice prior to prescribing. As with the contact

described above, these reminders will not contain any patient specific information and are designed as a personalized education step. No provider will receive more than three contacts in this way.

From initiation of educational messages until 9/20/2021, providers who receive one of the above educational messages will receive the message via email. Educational messages sent on or after 9/21/2021 will be sent via internal messaging within the EHR. This change in educational message delivery will allow for examination of best practices with providers.

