3. Description of use of the PDMP and study-associated BPAs, specifically monitoring
 - # of times PDMP activity/website is checked by site/practice/service, monthly, and specialty
 - Frequency of use of the PDMP one-click button per visit and per opioid prescription
 - Frequency of CDS and BPA trigger overall and per opioid prescription
 - Frequency of prescriptions for which the BPA would have fired but the prescriber had already checked the PDMP (look for change over time – do the BPAs lead to learning & change in prescriber behavior)
 - Number of times CDS alert fired, total and per visit (the alert is designed to only fire once during any encounter, thus the per visit rate will be <1)
 - Reviewed (via radio button or via alert)/unable to review/blank

- Resulted in signed Rx (reviewed/unable checked, signed prescription)
- Use of training tools and website. Identifying information on individuals accessing tools will not be recorded.
- Qualitative/semi-quantitative feedback from users as the CDS alerts are implemented

Patient specific measures will include:

- Number of controlled medication prescriptions, both within UCHealth and outside, based on PDMP data (including prescription details to include generic name, dosage, MMEs, days prescribed)
- Use of the PDMP by the prescriber prior to each controlled medication prescription written
- NarxCare risk score at the time of each prescription
- Number of providers/practices used for controlled substance prescriptions
- Number of pharmacies used for controlled substance prescriptions
- Diagnosis of any substance use disorder after the index visit date
- Accidental overdose of controlled substance after the index date (if data available)
- Patient demographics and clinical history characteristics

Educational outreach analysis: Alert firings for providers part of the educational outreach group will be analyzed for percent of non-compliant firings before outreach vs after as well as a comparison between the two different educational outreach efforts (email or EHR messaging system). Non-compliance is defined as 3 or more alerts for a single patient/encounter or >80% of firings closed using the comment/close option rather than using the PDMP link. Firings over time will be tracked as will changes in compliance before and after each outreach attempt. These data will be de-identified prior to reporting. Data will be examined for patterns based on demographics or work environment.

Calculation of sample size:

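### The over-80% limb of the non-compliance definition measures use of the alert's embedded link, not PDMP review, so a check by the one-click button after the alert scores as non-compliance

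*Combined protocol and SAP*

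**What the plan says.** Section IV.F, Educational outreach analysis, compares the "percent of non-compliant firings before outreach vs after" and also compares the two ways of sending the message, email and EHR messaging. It gives two limbs. The first is at encounter level: "Non-compliance is defined as 3 or more alerts for a single patient/encounter". The second is a share of firings: ">80% of firings closed using the comment/close option rather than using the PDMP link".

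Section IV.C describes the second type of reminder in different terms: "if a provider receives multiple alerts but does not access the PDMP in response, a reminder will be sent".

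Section IV.C also keeps a route to the PDMP outside the alert. For Arm 3, "One-click access to the PDMP for all patients will be maintained as in other arms", and Arm 4 has an equivalent statement. A check made early enough prevents the alert: "If the provider reviews the PDMP during the encounter before prescribing, the BPA will be suppressed". On the timing of attestation, the text says: "It can happen prior to prescription entry, in which case the alerts will not activate (suppression), or after activation of the alert".

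Among the PDMP and alert measures to be monitored, section IV.F lists whether review was recorded by radio button or through the alert, and whether a signed prescription resulted. The second limb uses neither.

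**The concern.** The reminder is aimed at providers who do not open the PDMP after an alert. The second limb scores how the window was closed. The two agree only if the embedded link is the sole way to reach the PDMP once the alert has fired, and the protocol says it is not. A provider who closes the alert and then uses the button has done what the reminder asks, yet each such firing counts towards the non-compliant share.

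What is at stake is the interpretation of the outreach comparison. The reminder tells providers that checking takes no more clicks than dismissing, which may itself steer them towards the link. If providers who already checked by button switch to the link, the analysis would credit the message with a gain in compliance although PDMP review had not changed. If that switching differed between email and EHR messages, the comparison of the two channels would be affected as well.

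**Working it through.** The plan states no sample size, power or expected rate for this analysis, so there is no figure to reproduce. The check is to read the sections together and then apply the rule.

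**1. Which checks are affected.**
- Check before the order (section IV.C): the alert is suppressed, no firing occurs, and nothing enters the numerator or denominator. Unaffected.
- Check through the alert's link: not a comment/close closure. Scored correctly.
- Comment/close, then a check by the one-click button: a comment/close closure. Scored as non-compliant although the PDMP was reviewed.
- Comment/close and no check: scored as non-compliant, as intended.

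Only the third case is misclassified.

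**2. The threshold.** For n firings, the rule needs the smallest k with k/n > 0.80.

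| Firings n | Closures k needed | k/n |
|---|---|---|
| 1 | 1 | 100% |
| 5 | 5 (4/5 is exactly 80% and does not pass) | 100% |
| 6 | 5 | 83.3% |
| 10 | 9 | 90% |
| 20 | 17 | 85% |
| 50 | 41 | 82% |

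No minimum number of firings is stated, so one closure in one firing meets the limb.

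**3. Close share against unreviewed share.** Let L be the share of firings handled by the link, B the share closed and then checked by button, and N the share closed with no check, with L + B + N = 1. The rule uses the close share, 1 − L = B + N. The reminder's target is N = 1 − L − B. The splits below are assumptions, because the documents give none.

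| L | B | Close share 1 − L | Flagged | Unreviewed share N |
|---|---|---|---|---|
| 0 | 1.00 | 100% | yes | 0% |
| 0.10 | 0 | 90% | yes | 90% |
| 0.10 | 0.30 | 90% | yes | 60% |
| 0.10 | 0.50 | 90% | yes | 40% |
| 0.10 | 0.80 | 90% | yes | 10% |
| 0.20 | 0 | 80% | no | 80% |
| 0.20 | 0.80 | 80% | no | 0% |

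The close share depends on L alone. The rule can therefore flag a provider with 10% unreviewed firings (L = 0.10, B = 0.80) and pass one with 80% unreviewed (L = 0.20, B = 0).

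**4. A change of route after a message.** If a share m (at most B) moves from button to link, the close share falls from 1 − L to 1 − L − m, while the reviewed share L + B stays the same. Starting at L = 0.10 and moving all of B:
- B = 0: close share stays at 90%; no artefact.
- B = 0.30: 90% to 60%; reviewed share 40% before and after.
- B = 0.50: 90% to 40%; reviewed share 60% before and after.
- B = 0.80: 90% to 10%; reviewed share 90% before and after.

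This reads a non-compliant firing as one closed by comment/close. The plan does not say so: the second limb describes a provider, the first an encounter, and the planned outcome is a percentage of firings. At provider level the artefact can be abrupt. With 10 firings, 9 closures are flagged and 8 are not, so moving one post-alert check from button to link removes the flag.

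**The case against.** The best defence is that the analysis evaluates messages about how alerts are handled. The reminder itself contrasts checking with dismissing, so link versus close is a reasonable process measure. PDMP review and prescribing are measured elsewhere. Closing the alert and then opening the button is the longer route, and nothing in the documents shows that anyone does it in more than 80% of firings. This stands in part. The close share is a fair usability measure, and the frequency of the problem is unknown. It does not justify calling the close share non-compliance when the stated target is failure to open the PDMP.

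A reader might infer more than the documents support:
- *That any alert closed without the link makes a prescriber non-compliant.* The limb requires more than 80% of firings and counts comment/close closures only. A single closure suffices only when firings are very few.
- *That abandoning the order is scored as non-compliant.* This would matter because hypothesis 2 is "Use of a focused CDS tool will decrease the percentage of high-risk patients who receive a controlled medication prescription". But the documents do not say how a dropped order is recorded. It is an undefined case, not a demonstrated misclassification.
- *That compliant prescribers are being sent reminders and using up their limit of three.* Section IV.C words the trigger as failure to access the PDMP. Nothing shows that the closure rule in section IV.F drives the messages.

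**Conclusion.** The mismatch is in the text. As written, the second limb measures use of the embedded link, and it misclassifies firings that were closed and then checked by the button. The error in the non-compliant share equals B, the share of firings handled that way. At a 90% close share, the true unreviewed share could be 90% (B = 0) or 10% (B = 0.80). A before/after fall as large as B could appear with no change in review. These sizes rest on assumed splits; the documents give no data on B.

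The effect is confined to the educational outreach analysis. A reader might suspect bias in the main trial results, but the primary outcome in section IV.A is the percentage of high-risk patients checked in the PDMP, and none of the listed outcomes uses this rule. The point is minor and worth a short clarification.

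**What to change.** In the outreach analysis of section IV.F:

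1. Count a firing as compliant if a PDMP review is recorded by any route (alert link or integrated button) in that encounter after the alert.
2. Report unable-to-review annotations as their own category; they are not a check. Report firings with no signed prescription separately too.
3. Keep the comment/close share as a descriptive usability measure.
4. Apply the definition to both message periods, email up to 9/20/2021 and EHR messaging from 9/21/2021, as an analysis change only. Leave the reminder trigger as it is: the document is dated 3 December 2021, so a new trigger would fall only in the EHR period and confound the comparison of channels.

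The cost is a few lines of text and one check of the data. Section IV.F already lists review by route and signed prescription as measures. However, section IV.E warns that fields stay blank when an alert is bypassed, while also saying that bypasses and utilization can be tracked. Firing-level linkage from alert to later review, including whether the radio-button record captures checks by the integrated button, must be confirmed first. Fewer firings will be classed as non-compliant, which leaves less to compare.

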2. Patients seeking care in the UCHealth system, who may receive an opioid prescription. The population will be limited to non-prisoners 12-89 years of age. Individuals with an active cancer diagnosis, sickle cell disease, or receiving specific end of life care are excluded. Pregnant women and decisionally challenged people will be included but are not considered a target population. No efforts will be made to include these individuals. Patients with limited literacy or limited English fluency will be included but are not considered a target population. Juveniles seen at providers included in the specialties of interest will be included (ages 12-17 inclusive) due to the inclusion of their health care provider. On the advice of pediatric toxicology experts, a cut point of 12 years of age is a clinically relevant age at which misuse of opioid analgesics and other controlled medications becomes a notable risk. However, no efforts will be made to target or enhance inclusion of juveniles. Pediatrics-only specialist offices will not be included in rollout of the CDS tools. Outcomes measures from juveniles will be examined separately from adults but may be included in the overall population if statistically appropriate.

C. Study Design and Research Methods

This will be a 1) cluster-randomized (by practice, as identified by a group of providers who work in the same department or set of departments within UCHealth) study for ambulatory/outpatient providers and 2) a randomized study (by provider) for emergency medicine and inpatient providers, with four study arms:

1. Arm 1: No change in practice
 - Providers are free to access the PDMP when prescribing via the existing integrated PDMP button.
 - This control group will enable monitoring of the secular changes in rates of controlled medication prescription within the UCHealth system.
 - In order to facilitate analysis of patient outcomes, CDS logic as in group 4 will run “silently” in this group such that risks are identified and recorded but not seen by the provider.
2. Arm 2: “Mandatory” use of the PDMP for all opioid prescriptions.
 - A best practice alert (BPA) will be triggered and fire when ordering an opioid prescription. The BPA will not appear (i.e. it will be suppressed) if the provider already reviewed the PDMP within the encounter. The BPA is shown in Figure 2 below.

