Provider specific rate of PDMP use	Total number PDMP searches for each provider, changes over time for each provider	Measures provider search behavior and variability changes for each CDS tool
Overall prescription rate after accessing PDMP	Number of times opioid/sedative/stimulant were prescribed after accessing the PDMP	Evaluate the impact of PDMP review on the decision to prescribe controlled medications
Provider demographics	Age, sex (M/F), years of employment (when available, data saved in EHR)	Evaluate variability in provider acceptance based on information stored in the EHR system.
Provider specific prescription rate after accessing PDMP	Total number of opioid/sedative/stimulant prescriptions divided by the number of times the provider accessed the PDMP for each provider	Evaluate provider variability in interpretation with and without decision support
Patient specific outcomes		
Patient demographics	Age, gender, ethnicity, insurance type	Description of patient population
Visit characteristics	Date of service [#] , service location, provider specialty, zip code	Evaluate visit for possible influences on patient and provider outcomes

Opioid prescription	Type, name, strength, number of pills, prescriber	Evaluate the effectiveness of the CDS tools
PDMP search completed	Yes/no	Evaluate the effectiveness of the CDS tools
Patient characteristics	Discharge diagnosis, past medical history, current co-morbid diagnoses, social history, other medications	Evaluate patient variability and other influences on prescribing/risk levels
CDS activation	Activation of CDS alert, which alert	Identify risk factors for patient as presented to prescriber
Prescriptions from PDMP	Type of medication (opioid, sedative, stimulant), date written [#] , date filled, [#] medication name, strength, formulation, # of pills prescribed, # of days supply, milligram morphine equivalents (MME), insurance type, pharmacy number	Evaluate patient outcome, needed for complete picture of prescription use
Non-UCHealth visits from All Payers Claims Data	ED visits, hospitalizations	Evaluate overall patient outcome, including unintended consequences of limitation of prescription pain medications
Provider Feedback		
Use of training materials and website	Usage (file access) over time	Measure of effectiveness of educational efforts

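### Counting prescriptions written after a PDMP access cannot show the impact of PDMP review on prescribing, because alert-prompted accesses occur only once an order is being placed

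*Combined protocol and SAP*

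**What the plan says.** In section IV.F, the data-to-be-collected table has a row for the overall prescription rate after PDMP access. Its definition is "Number of times opioid/sedative/stimulant were prescribed after accessing the PDMP" and its stated importance is "Evaluate the impact of PDMP review on the decision to prescribe controlled medications". Although it is called a rate, the row has no denominator, no comparator and no split by how the access came about.

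Section IV.C fixes when the alerts act. For Arm 2: "A best practice alert (BPA) will be triggered and fire when ordering an opioid prescription". For Arm 3: "BPA will be triggered upon entry of an opioid or benzodiazepine prescription and will fire only for patients determined to be at risk". Arm 4 uses the same trigger with added clinical criteria, and Figure 4 shows a controlled prescription as the trigger for all three visible alerts. Arm 1 has no visible alert. On the attestation of a PDMP check, the same section says: "It can happen prior to prescription entry, in which case the alerts will not activate (suppression), or after activation of the alert".

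Two other parts of section IV.F bear on the point. The system measures record the route of review, "Reviewed (via radio button or via alert)/unable to review/blank", and whether a signed prescription resulted. The table also lists prescriptions divided by visits, and section IV.A has a secondary outcome on the percentage of flagged patients who receive a controlled prescription. Neither of these last two depends on whether the PDMP was accessed.

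**The concern.** The row attaches a causal purpose to a measure taken only where the PDMP was accessed. Access is a behaviour after randomisation, and raising it is the aim of Hypothesis 1. The alerts also change which encounters enter the measure. A voluntary check can come before the prescriber has decided anything. A prompted check belongs to an encounter where an order is already being placed. The alert arms therefore gain accesses that are, by construction, close to a prescription.

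If the row is used for its stated purpose, an alert that causes some orders to be dropped can appear beside a higher figure for prescribing after review. A causal reading is not far-fetched here. Section III contrasts searched with unsearched patients in the earlier study (odds ratios 0.92 and 1.01 per additional prior prescription) and takes this to suggest that review affected prescribing.

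**Working it through.** The plan gives no value, model or sample size for this row, so there is no figure to reproduce. The check is a simple flow per 1,000 visits, with voluntary checking the same in both arms.

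**Inputs**

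- o = 0.20, share of visits with an intended order. Assumed; range examined 0.05 to 0.32. The upper end is 290,000 / 906,000 = 0.32 from the sample size text in IV.F, a per-patient figure over 20 months.
- v = 0.218, share of intended orders checked voluntarily beforehand. Borrowed from section III, where it is the probability of a check among patients prescribed an opioid under the earlier study's strictest criteria. It is not a control-arm baseline for this trial.
- u = 0.05, share of visits without an intended order that are checked. Assumed.
- a = 0.5, share of unchecked orders that are checked once the alert fires. Assumed.
- c = 0.20, share of reviewed orders dropped because of review. Assumed; review truly lowers prescribing.

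**Steps**

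- Intended orders: 1,000 × 0.20 = 200. Checked voluntarily: 200 × 0.218 = 43.6. Checks with no order intended: 800 × 0.05 = 40.
- Prompted checks in the alert arm: (200 − 43.6) × 0.5 = 78.2.
- Accesses: 43.6 + 40 = 83.6 without the alert; 83.6 + 78.2 = 161.8 with it.
- Prescriptions after access (the row as defined): 43.6 × 0.8 = 34.9 without; (43.6 + 78.2) × 0.8 = 97.4 with.
- All prescriptions: 200 − 0.2 × 43.6 = 191.3 without; 200 − 0.2 × 121.8 = 175.6 with.

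| Per 1,000 visits | No alert | Alert |
|---|---|---|
| Prescriptions after access (row as defined) | 34.9 | 97.4 |
| Share of accesses followed by a prescription | 34.88/83.6 = 41.7% | 97.44/161.8 = 60.2% |
| Prescribing in visits without access | 156.4/916.4 = 17.1% | 78.2/838.2 = 9.3% |
| All prescriptions per visit | 19.1% | 17.6% |

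Only the last line moves in the true direction. Using unreviewed visits as the comparator does not help: the gap between reviewed and unreviewed visits widens from 24.7 to 50.9 percentage points.

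**When the direction holds**

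The count rises by n × s, where n is the number of prompted checks and s the share of them signed, so it rises whenever both are above zero. The share of accesses becomes (34.88 + 78.2s)/161.8, which exceeds 41.7% only if s is above 41.7%, the signing share after voluntary checks. If 60% of prompted orders are dropped (s = 0.40), the share is (34.88 + 31.28)/161.8 = 40.9%, a slight fall. If u = 0 and review deters equally by either route, the share stays at 80% in both arms.

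A grid of 3,840 assumed settings used o 0.05 to 0.32, v 0.10 to 0.40, u 0 to 0.10, a 0.2 to 0.8, and deterrence 0.05 to 0.40 set separately for each route. The count rose and total prescribing fell in all of them. The share of accesses rose in 82%. That percentage describes the grid chosen and is not a probability.

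**The case against.** The strongest reply is that the trial already answers the prescribing question properly. Hypothesis 2, the secondary outcome in IV.A and the per-visit rate in IV.F do not condition on access, and the per-visit row is the one meant to show the overall impact of each tool. That stands: a reader might infer that the randomised prescribing comparison is compromised, and it is not.

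It is also fair that this is one row in a data table with no test, model or arm contrast attached, so the comparison between arms above is a possible use and not a stated one. Route of review and signed prescriptions are already to be recorded, and section IV.E concedes that dependence of prescribing on PDMP information cannot be settled definitively. What these replies leave in place is the row's own causal purpose. Nothing in the plan connects it to the unconditional measures or to the route data.

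Two further inferences go too far. One is that a working alert must make review look as if it raises prescribing. For a share of accesses this depends on signing being more common after prompted than after voluntary checks, which the documents do not establish. Voluntary checks in Arm 1 may also cluster around an intended order, which would narrow the gap. The other is that the per-provider row shares the bias. That row is "Total number of opioid/sedative/stimulant prescriptions divided by the number of times the provider accessed the PDMP for each provider", and because the alert inflates its denominator it moves the opposite way: 191.3/83.6 = 2.29 to 175.6/161.8 = 1.09 in the example.

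**Conclusion.** The point holds for this row. As defined, the measure cannot serve its stated purpose: with voluntary checking unchanged, the count rises in alert arms whenever prompted checks end in signed orders, whatever review does to prescribing. As a share of accesses it is biased upward if signing is more common after prompted than after voluntary checks. Its size, and in some settings its direction, cannot be derived from the documents, and the figures above are illustrations.

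The confirmatory comparisons are not touched. Nor does the statement in section G that PDMP use improves decisions rest on this row; it is a premise of the study. The matter is still worth correcting, because a stated measure that can point the wrong way is more than a missing detail.

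**What to change.** In this row, state that the impact on prescribing is judged by assigned arm, with all visits or eligible encounters as denominator (the per-visit rate already in the table), whether or not the PDMP was accessed. Keep prescribing after access as a descriptive figure only, with accesses as its denominator, split into review before order entry and review via the alert. The route and signed-prescription items already listed in section IV.F supply the data.

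Using assignment as an instrument to recover an effect of review itself is not advisable. The interruption, and the reminders described in section IV.C, could change prescribing without any review taking place.

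The cost is a few sentences of plan wording and a tabulation by route. The downside is that the row no longer supports a causal statement about review itself, only about the alerts as assigned.
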